9.4.2. Serious adverse events

A SAE is any untoward medical occurrence in a patient administered a medicinal or nutritional product (including pediatric formulas) at any dose that:

- Results in death;
- Is life-threatening;
- Requires inpatient hospitalization or prolongation of hospitalization (see below for circumstances that do not constitute AEs);
- Results in persistent or significant disability/incapacity (substantial disruption of the ability to conduct normal life functions);
- Results in congenital anomaly/birth defect.

Medical and scientific judgment is exercised in determining whether an event is an important medical event. An important medical event may not be immediately life-threatening and/or result in death or hospitalization. However, if it is determined that the event may jeopardize the patient or may require intervention to prevent one of the other outcomes listed in the definition above, the important medical event should be reported as serious.

Examples of such events are intensive treatment in an emergency room or at home for allergic bronchospasm; blood dyscrasias or convulsions that do not result in hospitalization; or development of drug dependency or drug abuse.

Additionally, any suspected transmission via a Pfizer product of an infectious agent, pathogenic or non-pathogenic, is considered serious. The event may be suspected from clinical symptoms or laboratory findings indicating an infection in a patient exposed to a Pfizer product. The terms "suspected transmission" and "transmission" are considered synonymous. These cases are considered unexpected and handled as serious expedited cases by PV personnel. Such cases are also considered for reporting as product defects, if appropriate.

Hospitalization

Hospitalization is defined as any initial admission (even if less than 24 hours) to a hospital or equivalent healthcare facility or any prolongation to an existing admission. Admission also includes transfer within the hospital to an acute/intensive care unit (e.g., from the psychiatric wing to a medical floor, medical floor to a coronary care unit, neurological floor to a tuberculosis unit). An emergency room visit does not necessarily constitute a hospitalization; however, an event leading to an emergency room visit should be assessed for medical importance.

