8.2.3.1. Adverse Reactions

- **Adverse reactions**

The number and proportion of patients with adverse reactions will be tabulated by SOC and PT.

- **Serious adverse reactions**

The number and proportion of patients with serious adverse reactions will be tabulated by SOC and PT.

- **Details of adverse reactions**

The number and proportion of patients with adverse reactions will be tabulated by SOC and PT for each of the following items.

- Seriousness [serious, non-serious]
- Expected/unexpected [Expected, unexpected]
- Intervention [discontinuation, temporarily discontinued or dose reduced]
- Outcome [not recovered, recovered with sequela, recovering, resolved/recovered, unknown]

In addition, the number and proportion of patients with adverse reaction that meets all of the following items will be tabulated by SOC and PT:

- The seriousness was considered “non-serious”;
- The intervention was “discontinuation”, “temporarily discontinued”, or “dose reduced”
- The outcome was “not recovered” or “recovered with sequela”.

If the same adverse reaction (the same PT) occurs more than once in the same patient, it will be handled as follows in the tabulation of the number of patients with events:

- Seriousness: If both serious and non-serious events are reported, “serious” will be adopted.
- Expected/unexpected: If both expected and unexpected events are reported, “expected” will be adopted.
- Number of days to onset: The number of days to the first event will be adopted
- Intervention: If multiple types of action are reported, one of discontinuation, temporarily discontinued or dose reduced, or other (none, dose increased), in descending order of precedence, will be adopted.
- Outcome: The outcome of the last occurring event will be used.

- **Safety specification items**

The number and proportion of patients with the following safety specification items will be tabulated.

- Central nervous system disorder
- Peripheral nerve disorders
- Aseptic meningitis
- Toxic epidermal necrolysis, oculomucocutaneous syndrome
- Acute pancreatitis

- Leukopenia, neutropenia
- Carcinogenicity

In addition, the number and proportion of patients who experienced each safety specification item will be tabulated by intervention and outcome, by SOC and PT.

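### For a repeated reaction the SAP pairs the highest-ranked action with the last outcome, which can mix occurrences or hide a sequela; the listed outcomes also include no fatal category

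*SAP*

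**What the plan says.** SAP 8.2.3.1 sets a rule for repeats: "If the same adverse reaction (the same PT) occurs more than once in the same patient, it will be handled as follows". Each attribute is then settled separately.

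- **Seriousness:** one serious occurrence makes the patient's record serious (the rule opens "If both serious and non-serious events are reported").
- **Action:** the highest-ranked action over all occurrences is kept: "Intervention: If multiple types of action are reported, one of discontinuation, temporarily discontinued or dose reduced, or other (none, dose increased), in descending order".
- **Outcome:** "Outcome: The outcome of the last occurring event will be used".

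Two outputs in the same section use action and outcome:

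- A three-condition table, for which "the number and proportion of patients with adverse reaction that meets all of the following items will be tabulated by SOC and PT". The conditions are that the reaction was non-serious, that the drug was stopped, interrupted or reduced, and that the outcome was not recovered or recovered with sequela.
- A table of the safety specification items by intervention and outcome.

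The outcome categories are given as "Outcome [not recovered, recovered with sequela, recovering, resolved/recovered, unknown", and none of them is fatal. SAP 7 sends a missing outcome to *unknown* but does not mention death. Protocol 9.4.2 puts "Results in death" first among its seriousness criteria, and Protocol 9.1 asks for autopsy findings when a patient dies.

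**The concern.** A table that requires an action and an outcome together is meant to describe one reaction. After the collapse, the two may belong to different episodes. The natural setting is a reaction that leads to interruption, followed by restart and recurrence. The SAP expects interruptions, since 8.2.2 defines treatment duration as dosing days net of suspension.

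The last-outcome rule causes a second problem, however the three-condition table is built. A sequela outlasts its episode. If a later episode of the same PT resolves, the outcome table shows recovery although the physician recorded lasting harm.

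The missing fatal category is a separate gap. The safety specification items tabulated by outcome include toxic epidermal necrolysis and acute pancreatitis, and nothing says in which row a fatal case belongs.

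At stake is the correct reading of a small number of clinically important cases in a safety study. The headline reaction rates are not affected.

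**Working it through.** The plan gives no figure for this rule, so the check is a logical enumeration. The study's one design figure does reproduce: 1 − 0.97^100 = 0.952, against the stated 95% for 100 patients and a true incidence of 3% (Protocol 7.5.2). It plays no part in what follows.

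**Inputs (SAP 8.2.3.1).** There are three action levels (discontinued; interrupted or reduced; other) and five outcomes (not recovered, sequela, recovering, resolved, unknown). Take two occurrences of one PT, both non-serious, so that only action and outcome vary.

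- Patterns per occurrence: 3 × 5 = 15. Ordered pairs: 15 × 15 = 225.
- A single occurrence meets the filter if an action was taken (2 levels) and the outcome is not recovered or sequela (2 levels): 2 × 2 = 4 of 15, leaving 11 that do not.
- Pairs in which at least one occurrence meets the filter: 225 − 11² = 104.

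**Filter applied to collapsed records (highest action, last outcome).**

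- *Missed:* the first occurrence meets the filter (4) and the second has one of the three other outcomes with any action (3 × 3 = 9). 4 × 9 = 36.
- *Wrongly counted:* the first has an action and another outcome (2 × 3 = 6); the second has no qualifying action and is not recovered or has a sequela (2). 6 × 2 = 12.
- *Collapsed pair seen in neither occurrence:* the first action ranks strictly above the second (3 ways) and the outcomes differ (5 × 4 = 20). 3 × 20 = 60.

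**Outcome table alone.** Pairs with a sequela in at least one occurrence: 225 − 12² = 81. The sequela is overwritten when it comes first and the second outcome differs: 3 × 1 × 3 × 4 = 36.

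**Examples.**

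| First occurrence | Second occurrence | Collapsed record | Effect |
|---|---|---|---|
| interrupted, sequela | no action, resolved | interrupted, resolved | sequela lost; patient missed |
| reduced, resolved | no action, not recovered | reduced, not recovered | counted although neither occurrence met the filter |

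**Alternative rules.** Testing the filter within each occurrence gives no missed and no false entries, by construction. Changing only the outcome rule, from last to worst, gives no misses but 2 × 6 × 2 = 24 false entries, because action and outcome can still come from different occurrences.

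**Fatal outcome.** SAP 7 covers missing outcomes only, and a death is not a missing outcome. None of the five categories describes it. The three-condition table is limited to non-serious reactions, so this gap concerns the general outcome table and the safety specification table.

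**The case against.** The strongest reply is that the SAP never says the three-condition filter follows the collapse. It speaks of a reaction, in the singular, meeting all the items, which can be read as a test of each occurrence. This stands as a limit: the 36 and 12 arise only under the other reading. That reading is still the natural one, because the repeat rule comes directly after the table's definition and governs counts of patients with events.

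A reader might take (36 + 12)/225 = 21% as an error rate. It is not one. The patterns are unweighted, and many are unlikely. Observation ends with treatment (Protocol 7.2.6) and the safety analysis rests primarily on that period (SAP 8.2.3), so a recurrence after discontinuation is largely excluded. A first episode that never recovered has hardly recurred. Removing both leaves 1 × 9 = 9 missed and 3 × 2 = 6 wrongly counted patterns.

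The last outcome is also a defensible measure of final status. The SAP has no uniform worst-case convention for this rule to break, since for repeats it keeps *expected* over *unexpected*. A worst-outcome rule would show as not recovered a patient who eventually recovered. This stands against replacing the rule wholesale, but it does not answer the case of a sequela, which a later resolved episode does not undo.

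On deaths, a reader might infer that a fatal reaction would vanish from the report. The documents do not support that. It would appear in the serious-reaction and serious-event tables (SAP 8.2.3.1 and 8.2.3.2) and in the listings (SAP 9). Nor is the outcome list certainly closed: the neighbouring intervention list omits the *other* level that the repeat rule uses, and Protocol 7.3.7 names the outcome item without its codes. What remains is that the SAP gives a death no stated row.

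**Conclusion.** The point holds in limited form. On the natural reading of SAP 8.2.3.1, the three-condition table can miss a patient who had a qualifying reaction or count one who had none. The safety specification table, if action and outcome are cross-classified, can likewise mix occurrences. Whichever way those tables are built, the outcome table can show recovery over an earlier recorded sequela, and a fatal reaction has no stated category.

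The effect reaches only patients with a repeated PT, and any death. The documents do not say how often either occurs, so no expected number can be given. If the safety set has the planned 100 patients and is the denominator, one such patient moves a cell of these tables by 1/100, or one percentage point. Incidence by PT is unchanged, because the patient is counted once under any outcome rule. The conclusion about the three-condition table assumes that the filter is applied after the collapse.

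**What to change.** In SAP 8.2.3.1:

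1. State that the three-condition filter is applied to each occurrence, and that a patient is counted if any single occurrence meets all three conditions. State likewise that any cross-tabulation of action by outcome for the safety specification items uses pairs from the same occurrence.
2. Add *fatal* to the outcome categories.
3. Keep the last-outcome rule if preferred, but do not let a later resolved episode overwrite an earlier recovery with sequela. One way is to show the worst outcome beside the last, with a stated ranking that includes *unknown*.

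The third change alone would not mend the three-condition table, so the first is needed as well. The cost is a few lines of wording and minor programming. The outcome table may look slightly less favourable.

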7.2.6. Observation period

The observation period shall start on the day the treatment with this drug begins and end on the day the treatment is completed; however, it shall be cut off at Week 8 after the initiation of treatment (Day 56 counting from Day 1 as the day the treatment begins) if the treatment is prolonged.

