8.2.2. Patient Background and Treatment History of Anametro

- **Patient background**

In the safety analysis set, clinical response analysis set, and microbiological response analysis set, the following patient background factors will be tabulated in accordance with Section 8.1.

- Sex [male, female]
- Age (continuous)
- Age group [<15 years, ≥ 15 to <65 years, ≥ 65 years]
- Age group [≥ 10 to <20 years, ≥ 20 to <40 years, ≥ 40 to <65 years, ≥ 65 to <70 years, ≥ 70 to <75 years, ≥ 75 years]
- Inpatient/outpatient status at the first prescription [inpatient, outpatient]
- Body weight (continuous)
- Body Mass Index (continuous)
- Diagnostic name* (anaerobic infection, infectious enterocolitis, amebic dysentery, others)
- Detailed diagnosis name of anaerobic infection
- Severity [mild, moderate, severe, unknown]
- Hepatic dysfunction [absent, present]
- Renal dysfunction [absent, present]
- Past medical history other than hepatic/renal dysfunction [absent, present]
- Concurrent illness other than hepatic/renal dysfunction [absent, present]
- Prior treatment (medication for infection) [absent, present]
- Concomitant medication (medication for infection) [absent, present]

* The same patient may have multiple diagnoses. In such case, additional categories may be added (e.g., anaerobic infection plus infectious enterocolitis).

In addition, patient background will also be tabulated by maximum number of daily doses and by the presence or absence of a central nervous system disorder.

In the safety analysis set, the number and proportion of the following patients will be tabulated by SOCs and PTs of MedDRA.

- Past medical history other than hepatic/renal dysfunction

- Concurrent illness other than hepatic/renal dysfunction.

In the safety analysis set and clinical response analysis set, the number and proportion of the following patients will be tabulated.

- Presence or absence of pregnancy
- Concomitant medication (medication for infection)
- Prior treatment (medication for infection)

- **Status of treatment of Anaemetro**

In the safety analysis set, the following status of treatment of Anaemetro will be tabulated:

- Duration of treatment (continuous)
- Duration of treatment (1) [1, 2, 3, 4, 5, 6, 7, 8, 9, 10, 11, 12, 13, 14, 15, 16, 17, 18, 19, 20, 21, ≥ 22 days]
- Duration of treatment (2) [≤ 3 day, ≥ 4 to ≤ 7 days, ≥ 8 to ≤ 14 days, ≥ 15 to ≤ 21 days, ≥ 22 days]
- Duration of treatment (3) [≤ 3 days, ≥ 4 to ≤ 10 days, > 10 days]

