- Maximum dose per single dose [< 500 mg, 500 mg, > 500 mg]
- Mean dose per single dose [< 500 mg, 500 mg, > 500 mg]
- Mean dose per single dose (continuous)
- Maximum number of daily doses [1, 2, 3, 4, > 4 times]
- Mean number of daily doses [< 1 time, 1 time, > 1 to < 2 times, 2 times, > 2 to < 3 times, 3 times, > 3 to < 4 times, 4 times, > 4 times]
- Mean number of daily doses (continuous)
- Dose escalation [absent, present]
- Overdose [absent, present].

The duration of treatment is from the initial day of administration in this Study to the last confirmed day of administration, and is the actual dosing days that excludes the period during which Anaemetro is suspended.

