8.2.3. Safety Analysis

Safety analysis will be primarily based on the data collected during the observation period that is from the start of Anaemetro administration to the end of Anaemetro administration.

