In order to explore factors common to those who experienced the safety specification items, listings of patient background and concomitant medications for patients who experienced the most frequent safety specification items will be tabulated.

- **Time to adverse reaction**

The number of patients who experienced an adverse reaction will be tabulated by time to first development (≤ 3 days, ≥ 4 to ≤ 10 days, > 10 days), by SOC and PT.

- **Adverse reactions by patients of included/excluded in the safety analysis set**

In completed patients, the listing of adverse reactions in patients excluded from the safety analysis set will be prepared. In addition, the number of patients with events will be tabulated by SOC and PT.

- **Adverse reactions that developed within and outside the observation period**

Using the safety analysis set, the number of patients with adverse reactions will be tabulated by whether each reaction developed within or outside the observation period, by SOC and PT.

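### Time to first adverse reaction is tabulated as counts only, so the table cannot separate when risk occurs from how long patients were treated

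*SAP*

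**What the plan says.** SAP 8.2.3.1, under time to adverse reaction, plans this: "The number of patients who experienced an adverse reaction will be tabulated by time to first development". The categories are "≤ 3 days, ≥ 4 to ≤ 10 days, > 10 days), by SOC and PT". No proportion, number at risk, patient-time, rate or cumulative incidence estimate is planned for onset, there or elsewhere in the SAP.

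Protocol 7.2.6 sets the observation period to "start on the day the treatment with this drug begins and end on the day the treatment is completed", with a cut-off at "Day 56 counting from Day 1 as the day the treatment begins". SAP 8.2.3 bases the safety analysis primarily on "the observation period that is from the start of Anaemetro administration to the end of Anaemetro administration".

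SAP 8.2.2 separately tabulates treatment duration in the safety analysis set with the same cut points: "Duration of treatment (3) [≤ 3 days, ≥ 4 to ≤ 10 days, > 10 days". Duration there "is the actual dosing days that excludes the period during which Anaemetro is suspended". The SAP does not link this table to the onset table.

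**The concern.** A patient can contribute a first on-treatment reaction to an interval only if still under observation and still free of the reaction. Observation stops with treatment, so that group shrinks from one interval to the next. The intervals also differ greatly in length. A count of first reactions per interval therefore reflects three things together: the daily risk, the number of patients still exposed, and the length of the window.

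An onset table is naturally read as showing whether reactions come early or late, and whether risk changes with continued treatment. Protocol 6.1 names central nervous system disorder as the important identified risk, and Protocol 6 sets out to examine its tendency in practice. Counts alone cannot support a reading in either direction.

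**Working it through.** **Figures in the plan.** The onset table has no stated figure to reproduce. The sample size statement (Protocol 7.5) does reproduce: 1 − 0.97^100 = 0.952, so 100 patients give about a 95% chance of seeing at least one case of a reaction with 3% incidence.

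**Interval lengths.** Days 1–3 are 3 days and Days 4–10 are 7 days. Day 11 to the Day 56 cap is 56 − 10 = 46 days at most.

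**Assumptions.** The documents give neither the distribution of treatment duration nor a daily reaction rate. I assume 100 patients (the planned size), a constant rate of 2 first reactions per 100 patient-days, and exponential durations with median m days, cut at Day 56.

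**Formula.** Patients at risk on Day d = 100 × 0.5^((d−1)/m) × 0.98^(d−1). Expected first reactions on that day = 0.02 × patients at risk. Sum over the days of each interval.

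**Worked case, m = 3, Days 1–3.** Patients at risk are 100, 77.8 and 60.5, which is 238.3 patient-days. Expected count = 0.02 × 238.3 = 4.8.

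**Results with the daily risk constant throughout:**

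| Median duration | Expected counts, Days 1–3 / 4–10 / 11–56 | Patient-days | Shape of the counts |
|---|---|---|---|
| 3 days | 4.8 / 3.5 / 0.7 | 238 / 175 / 36 | falling |
| 5 days | 5.2 / 5.7 / 2.8 | 258 / 284 / 139 | humped |
| 7 days | 5.4 / 7.0 / 5.4 | 268 / 352 / 269 | humped |
| 10 days | 5.5 / 8.3 / 9.4 | 275 / 416 / 469 | rising |
| 14 days | 5.6 / 9.3 / 14.2 | 280 / 465 / 710 | rising |

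Dividing counts by patient-days returns 2.0 per 100 in every cell.

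**Sensitivity to the shape of the durations.** With less spread-out durations (Weibull, shape 2) and the same constant rate, the counts are 5.6/5.1/0.2 at a median of 5 days, 5.8/9.6/4.3 at 10 days and 5.8/10.9/9.2 at 14 days. The apparent pattern changes again while the daily risk does not.

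**Would the number at risk alone be enough?** No. At m = 3, patients at risk at the start of each interval are 100, 100 × 0.5 × 0.98^3 = 47.1, and 100 × 0.5^(10/3) × 0.98^10 = 8.1. The interval proportions are 4.8/100 = 4.8%, 3.5/47.1 = 7.5% and 0.73/8.1 = 9.0%. Under a constant daily risk these rise, because the later windows are longer. Patient-days or a cumulative incidence estimate is needed.

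**The case against.** The strongest defence is that the table claims little. It describes onset times among affected patients. SAP 4.1 calls the tests exploratory, SAP 4.2 has no decision rules, and the main safety result is incidence per event. That stands, and it limits the weight of the point.

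Second, the duration table has the same cut points, so a reader could approximate the number still treated at each interval start: everyone, everyone minus the shortest-duration group, and the longest-duration group. The exposure and adverse reaction listings (SAP 9) would also help. This mitigates only in part. Duration counts dosing days with suspensions removed, whereas observation runs on calendar days, and the SAP does not say which clock onset uses. If onset is in calendar days, a patient with a suspension can have an onset after Day 10 and a duration of 10 days or less. The duration table also gives no patient-days by interval. Its failure to remove patients who have already reacted matters little when reactions are few.

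Third, estimates will be imprecise. Exact Poisson 95% limits for x events are χ²(0.025; 2x)/2 and χ²(0.975; 2x+2)/2. Five events in 238 patient-days give 2.1 per 100 (0.7 to 4.9), and one event in 36 patient-days gives about 2.8 (0.1 to 15). That is a reason to limit the addition to two outcomes and to show the intervals. It does not justify bare counts, which hide the same imprecision.

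A reader might infer more: that the table will make a rising risk look like a falling one, and that unequal intervals are the cause. The documents do not support this. It can happen: with rates rising 2.0, 2.5, 3.0 per 100 patient-days and a median of 3 days, expected counts are 4.8/4.3/1.0. With the same rates and a median of 10 days (exponential) they are 5.5/10.3/12.3, a steeper rise than the true one. Any false fall comes from patients leaving as treatment ends. Longer later windows collect more events and work against it.

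**Conclusion.** The point holds as a limit on interpretation. Counts in windows of 3, 7 and up to 46 days, drawn from a shrinking group, cannot show how daily risk changes with time on treatment. In the illustration, one constant daily risk gives falling, humped or rising counts as the assumed median duration goes from 3 to 14 days.

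The size and direction rest on assumed durations and an assumed rate, because the documents give neither. They therefore do not support a claim that the table would hide a rise in particular. What rests on the documents alone is that observation ends with treatment, that the intervals are unequal, and that no denominator is planned. The duration table narrows the gap without closing it. This is a cheap improvement to a descriptive table in a study of about 100 patients, and no primary result changes.

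**What to change.** In SAP 8.2.3.1, for any adverse reaction and for CNS disorder, add for each onset interval:

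- the number of patients under observation and free of the reaction at its start;
- the patient-days at risk within it;
- the first-reaction rate per 100 patient-days, with an exact 95% CI.

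Alternatively, give a cumulative incidence estimate with numbers at risk, and state how end of treatment is handled. CNS disorder needs its own row, because SAP 6.1 defines it by a CRF check mark and not by SOC or PT. State whether onset is counted in calendar days from Day 1, and use the same clock for patient-days. Do not compare interval proportions across the unequal windows. The SOC and PT breakdown can stay as counts.

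The cost is a few derived columns. Treatment start and end dates (Protocol 7.3.2) and event onset dates (Protocol 7.3.7) are already collected. The intervals will be wide because few events are expected, and the report should say so.
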